## 2 INTRODUCTION

### 2.1 Study Rationale

Drug development for symptomatic therapies in AD is burdened by significant time and cost to assess the potential efficacy of new drugs. Proof-of-concept studies for new drugs rely on demonstrating improvement on clinical cognition measures such as the ADAS-Cog. However, many of these clinical endpoints are bound by limited sensitivity to disease progression and/or drug response. As a result, large sample sizes and long treatment duration (typically  $\geq 3$ -6 months) are required to provide sufficient statistical power to begin to establish efficacy. Moreover, pathophysiological changes secondary to AD lead to cognitive fluctuations that create variability in patient cognitive performance and thus in assessment of cognition endpoints. Thus, assessment of cognitive pharmacodynamic effects using these standard measurements in small patient populations is not feasible.

Consequently, there is an urgent need for novel clinical trial methodology that will support high-predictive value decision-making in the early clinical development environment to trigger investment in fully-powered symptomatic trials. The rationale for this study is to assess whether one candidate methodology is viable. This methodology would have the ability to interrogate and assess probability of benefit of pro-cognitive effects of investigational compounds in a relatively low number of patients affected by AD pathology, in a relative rapid manner to improve clinical throughput, make better Phase 1 triaging decisions across different mechanisms, and reduce the number of low-probability of success compounds advanced for testing in Phase 2.

### 2.2 Background

The overall objective of this study is to rigorously test a novel high-frequency “burst” testing paradigm designed to leverage the repeatability of computerized batteries for a precise assessment of cognitive capability, as a means to assess pro-cognitive pharmacodynamic potential in one or two key sentinel cognitive domains with strong face validity for predicting efficacy in more standard assessment tools. Donepezil will be used as the investigational agent in this study as it is the most commonly prescribed cholinesterase inhibitor prescribed for symptomatic treatment of AD. As such, it is anticipated that treatment effect data on donepezil obtained through this study can be used as benchmarking data for evaluation of performance of future pro-cognitive compounds being assessed using this high-frequency testing paradigm.

#### 2.2.1 Information on Study-Related Therapy

The most common AEs of donepezil, defined as those occurring at a frequency of at least 5% in patients receiving 10 mg/day and occurring at twice the rate observed in placebo treated participants, are largely predicted by the cholinomimetic effects of donepezil HCl. These include nausea, diarrhea, insomnia, vomiting, muscle cramps, fatigue and anorexia. These AEs are typically of mild intensity and transient, resolving during continued donepezil HCl treatment without the need for dose modification [Jackson, S., et al 2004]. Less-commonly

observed AEs include depression and sleep disturbances (e.g., abnormal dreams and somnolence).

Donepezil is ~ 96% bound to human plasma proteins, mainly to albumins (~ 75%) and alpha-1 acid glycoprotein (about 21%) over the concentration range of 2 to 1000 ng/mL. Donepezil is both excreted in the urine intact and extensively metabolized to four major metabolites, two of which are known to be active, and a number of minor metabolites, not all of which have been identified. Donepezil is metabolized by CYP 450 isoenzymes 2D6 and 3A4 and undergoes glucuronidation. Donepezil has a Tmax of ~3 to 4 hours and half-life ~ 70 hours.

Refer to the approved labeling for additional detailed background information on donepezil [U.S. Prescribing Information 2018].

### 2.3 Benefit/Risk Assessment

It cannot be guaranteed that participants in experimental medicine will directly benefit from participation, as these studies are designed to provide information about the safety and effectiveness of an investigational procedure.

Additional details regarding specific benefits and risks for participants participating in this clinical study may be found in the informed consent documents.

## 3 HYPOTHESES, OBJECTIVES, AND ENDPOINTS

The following objectives will be evaluated in participants diagnosed with mild cognitive impairment or mild Alzheimer's Disease.

| Objectives   | Endpoints   |
|--|---|
| Primary  |   |
| 

To assess the ability of a repeated high-frequency site-based computerized cognitive assessment to evaluate the potential treatment effects of donepezil compared with placebo in participants with MCI/mild AD following a limited treatment duration (8 weeks treatment).

 
Hypothesis: After 8 weeks of daily treatment, the change from the placebo run-in period (Week -1) in average proportion of correct responses on the One Card Learning (OCL) task (a task of visual learning) in participants receiving donepezil compared with participants receiving placebo will be <math>\geq 2</math> percentage points.
 | 

Proportion of correct responses on the OCL task at Weeks -1, 2, 4, 6, and 8

 |

| Objectives   | Endpoints   |
|--|---|
| Secondary  |   |
| 
 
To characterize the inter- and intra-subject variability associated with repeated high-frequency site-based computerized cognitive test administration in participants with MCI/mild AD.
 
 
Hypothesis: The overall standard deviation associated with the change from the placebo run-in period in average OCL repeated measurements (arcsine square root transformed) after 8 weeks of donepezil treatment is <math>\leq 0.1</math>.
  | 
 
Proportion of correct responses on the OCL task
 
 |
| 
 
To assess the ability of a repeated high-frequency site-based computerized cognitive assessment to evaluate the potential treatment effects of donepezil after 8 weeks of treatment compared to after the placebo run-in period in participants with MCI/mild AD.
 
 
Hypothesis: After 8 weeks of daily treatment in participants receiving donepezil, the proportion of correct responses in the OCL task will improve relative to performance during the placebo run-in period by a clinically-meaningful (>2 percentage points) degree of change.
 | 
 
Proportion of correct responses on the OCL task
 
 |

| Objectives   | Endpoints  |
|--|--|
| Tertiary/Exploratory   |  |
| 
 
To characterize the inter- and intra-subject variability associated with repeated high-frequency site-based computerized cognitive test administration in participants with MCI/mild AD.
 
   | 
 
Detection (DET), Identification (IDN), One Back (ONB), International Shopping List Test (ISLT), Modified Groton Maze Learning Test (GMLTM), Continuous Paired Associate Learning (CPAL), International Daily Symbol Substitution Test - Medicines (IDSSTM), International Shopping List Test - Delayed Recall (ISRL) at Weeks -1, 2, 4, 6, and 8
 
 |
| 
 
To assess the ability of a repeated high-frequency site-based computerized cognitive assessment to evaluate the potential treatment effects of donepezil after 8 weeks of treatment compared to after the placebo run-in period in participants with MCI/mild AD.
 
  | 
 
DET, IDN, ONB, ISLT, GMLTM, CPAL, IDSSTM, ISRL at Weeks -1, 2, 4, 6, and 8
 
   |
| 
 
To assess the ability of a repeated high-frequency site-based computerized cognitive assessment to evaluate the potential treatment effects of donepezil compared with placebo on tests associated with cognitive domains of attention, executive function and verbal/ visual memory in participants with MCI/ mild AD following 8 weeks of treatment.
 
 | 
 
DET, IDN, ONB, ISLT, GMLTM, CPAL, IDSSTM, ISRL at Weeks -1, 2, 4, 6, and 8
 
   |
| 
 
To evaluate the psychometric properties of the Face-Name Associative Memory Exam (FNAME) as a measure of learning.
 
   | 
 
FNAME
 
  |
| 
 
To establish the operational feasibility of frequent site-based administration of cognitive function testing in participants with MCI/mild AD.
 
   | 
 
Study Execution
 
  |

| Objectives   | Endpoints  |
|--|--|
| 
 
To assess participants' and study partner/informants' perception and comfort with the use of at-home device (e.g. tablet/computer) in future studies.
 
  | 
 
Questionnaires
 
   |
| 
 
To evaluate the differences in baseline cognitive performance and response to donepezil treatment (comparison to placebo and to pre-treatment baseline) between different participant subgroups defined by positive and negative results for various exploratory plasma biomarkers for AD diagnosis.
 
 | 
 
Plasma levels of beta-amyloid and phospho-tau isoforms
 
   |
| 
 
To assess within-subject test-retest reliability of various exploratory plasma biomarkers for AD diagnosis in replicate samples taken during the study.
 
  | 
 
Plasma levels of beta-amyloid and phospho-tau isoforms
 
   |
| 
 
To explore the relationship between genetic variation and response to the treatment(s) administered, and mechanisms of disease. Variation across the human genome may be analyzed for association with clinical data collected in the study.
 
   | 
 
Apolipoprotein E (APOE) genotyping
 
Germline genetic variation and association to clinical data collected in this study.
 
 |

## 4 STUDY DESIGN

### 4.1 Overall Design

This is a randomized, placebo-controlled, parallel-group, multi-site study to evaluate the effects of donepezil 10 mg PO daily on cognitive function using a high-frequency site-based computerized cognitive assessment, the Cogstate Computerized Battery, in participants with MCI or mild AD.

The study will enroll approximately 36 participants randomized to receive over-encapsulated donepezil or placebo in a 2:1 ratio following a single blinded run-in period with placebo. No formal stratification is planned per site; however, an allocation schedule with separate panels for disease status (ie, Panel A for MCI and Panel B for mild AD) will be used with each panel incorporating randomization in a 2:1 ratio. Efforts will be made to enroll a minimum of 12 participants meeting AD diagnostic criteria (Panel B) in this study. The number of participants per panel (ie, disease status) may be adjusted by the Sponsor based on

enrollment metrics to ensure timely study completion, but the total sample size of the study will remain at approximately 36. The rationale for ensuring this minimum number of participants meeting AD criteria is that prior data suggest a more robust treatment signal for OCL testing in this population, and ensuring adequate representation of mild AD in the overall study sample will increase probability of study success.

Potential participants will have a Screening Visit (V1) to determine if they meet inclusion and exclusion criteria. Following the Screening Visit, participants will have a Baseline/Familiarization Visit (V2), during which the Cogstate battery will be administered for familiarization purposes as described in Section 1.3 (SoA). Participants who met the selection criteria at that point will return for 2 additional visits (V3 and V4) during that week, when a Cogstate battery as described in Section 1.3 (SoA) will be administered to further acclimate them to the high-frequency testing paradigm, and to provide a standard replicate testing period consistent with a mock baseline assessment initiating the placebo run-in period. As part of the testing during this week, participants will also undergo additional paper/pencil cognitive baseline (pre-treatment) assessment for the purposes of characterization of baseline cognitive status across several different performance domains before randomization into one of two treatment sequences.

After the Randomization Visit (V4), participants will enter a single-blind placebo run-in period of approximately 2 weeks. During the second week of the placebo run-in period, participants will undergo a high-frequency testing period with a Cogstate battery as described in Section 1.3 (SoA). This testing period will cover 3 clinic visits (V5-7) over the span of 5 consecutive days. Testing will be administered on-site.

After completing the placebo run-in period, participants will enter a double-blind intervention period of approximately 8 weeks and initiate treatment with either over-encapsulated donepezil or placebo. Participants allocated to donepezil will be given donepezil 5 mg PO daily for approximately 2 weeks (at least 14 days), followed by titration to donepezil 10 mg PO daily depending on tolerability. Once titrated to donepezil 10 mg PO daily, participants will remain on this daily dose for 6 weeks. To maintain the study blind, participants allocated to placebo will follow the same dose titration regimen. Participants will return to the clinic at two-week intervals during the treatment period, to undergo computerized Cogstate testing following the high-frequency schedule as described in Section 1.3 (SoA) (at V8-10, V11-13, V14-16, and V17-19). The paper/pencil based cognitive battery (which was administered at baseline prior to randomization) will be administered a second time at the End of Treatment Visit (V19). A Post-Study Visit (V20) will be conducted at least 14 days after the last dose of study drug.

This protocol is written with flexibility to accommodate the inherent dynamic nature of Phase 1 clinical studies. Refer to Section 8.10.5 for examples of modifications permitted within the protocol parameters.

Specific procedures to be performed during the study, as well as their prescribed times and associated visit windows, are outlined in the SoA in Section 1.3. Details of each procedure are provided in Section 8.

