## **5 STUDY POPULATION**

Treatment-naïve male/female participants with MCI or mild AD between the ages of 55 and 85 years (inclusive) will be enrolled in this study. Inclusion of participants above the age of 80 years will need Sponsor's approval before enrollment. Efforts will be made to enroll at least one-third of the participants meeting mild AD in this study.

Prospective approval of protocol deviations to recruitment and enrollment criteria, also known as protocol waivers or exemptions, is not permitted.

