### 6.3 Measures to Minimize Bias: Randomization and Blinding

#### 6.3.1 Intervention Assignment

Participants will be assigned randomly according to a computer-generated allocation schedule.

The sample allocation schedule is shown in [Table 4](#).

Table 4 Sample Allocation Schedule

|             | Sample Size (N) | Run-In Period | Intervention Period |
|-------------|-----------------|---------------|---------------------|
| A (MCI)     | 16              | Placebo       | Donepezil           |
| A (MCI)     | 8               | Placebo       | Placebo             |
| B (Mild AD) | 8               | Placebo       | Donepezil           |
| B (Mild AD) | 4               | Placebo       | Placebo             |

AD=Alzheimer's disease; MCI=mild cognitive impairment

The suggested sample size per treatment sequences and panel maybe adjusted by the sponsor based on enrollment metrics to ensure timely study completion. The allocation schedule will include additional allocation numbers per panel to enable flexibility to enroll more MCI (n >24) or more mild AD (n >12) participants as determined by the sponsor, but the total sample size of the study will remain approximately 36 participants. Participants may be replaced as needed to ensure that approximately 36 evaluable participants complete the study as described in Section 9.9.

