## 9.6 Statistical Methods

The primary hypothesis is related to proportion of correct response in the OCL task associated with change from placebo run-in period (Week -1) at Week 8 for donepezil group compared with placebo group. To assess the primary hypothesis, the repeated measurements

associated with proportion of correct response in the OCL task at each of Weeks -1, 2, 4, 6 and 8 will be averaged by each participant. Intermittent missing repeated measures within a time point (e.g., Week 2) will not be imputed and data will be averaged as available. Observations with integrity failures will be excluded from analysis and will not be imputed. The amount and patterns of missing data will be summarized. Change from placebo run-in period in the average correct response of OCL measurements will be estimated using a linear mixed effects model containing fixed effects for Week, proportion of correct response in the OCL measurement at baseline (placebo run-in period), Treatment (donepezil/placebo) and Week by Treatment interaction with an unstructured covariance matrix which will account for missing data under a missing at random assumption. Least square variances will be estimated for change from placebo run-in period by treatment group (donepezil/placebo) and Week 8 using above mentioned linear mixed models. The posterior distribution of the variances will be estimated by generating 10,000 independent draws from non-informative Inverse Gamma prior for both treatment groups. Conditioned on each variance, difference of average correct response rate of OCL task from placebo run-in period will be generated from a Normal distribution with mean equal to the estimated least square mean estimate for both groups at Week 8. The posterior probability of true mean difference between donepezil and placebo group at Week 8 relative to Week -1 is greater than 2 percentage points will be derived from the posterior distribution. We can rewrite the model as following

$$\sigma^2 \sim \text{Inverse Gamma}(\alpha, \beta), \text{ where } \alpha = \beta = 0.0001$$
$$\sigma_{trt}^2 | y_{iw} \propto \text{Inverse Gamma} \left( \alpha + \frac{n_{trt}}{2}, \beta + \frac{n_{trt}}{2} S_{trt}^2 \right), \text{ where } trt = \text{donepezil, placebo}$$
$$y_i | \cdot \sim \text{Normal}(\hat{\mu}_{trt}, \sigma_{trt}^2 | \cdot), \text{ where } i = \begin{cases} 1, \dots, 24 & \text{when } trt = \text{donepezil} \\ 1, \dots, 12 & \text{when } trt = \text{placebo} \end{cases}$$

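### Section 4.1 expects a stronger OCL signal in mild AD and the sponsor may change the MCI/mild-AD mix, yet Section 9.6 omits disease status and reports only one pooled Week 8 difference

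*Combined protocol and SAP*

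**What the plan says.** **Target and its reason.** Section 4.1: "Efforts will be made to enroll a minimum of 12 participants meeting AD diagnostic criteria (Panel B) in this study". Section 5 restates it as a share: "Efforts will be made to enroll at least one-third of the participants meeting mild AD in this study". The reason in Section 4.1 is that "prior data suggest a more robust treatment signal for OCL testing in this population", and that "ensuring adequate representation of mild AD in the overall study sample will increase probability of study success".

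**Freedom to change the mix.** The same paragraph of Section 4.1 says "The number of participants per panel (ie, disease status) may be adjusted by the Sponsor based on" enrolment metrics. In Section 6.3.1 the sizes by panel and sequence "maybe adjusted by the sponsor based on enrollment metrics to ensure timely study completion", and spare allocation numbers are provided "to enable flexibility to enroll more MCI (n >24) or more mild AD (n >12) participants as determined by the sponsor". Both sections keep the total at approximately 36. Neither gives a cap or a binding floor.

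**Analysis.** Section 6.3.2 names disease status as the stratification factor, and Section 4.1 randomises 2:1 within each panel. The primary model in Section 9.6 has fixed effects for week and baseline OCL, then "Treatment (donepezil/placebo) and Week by Treatment interaction with an unstructured covariance matrix". It has no disease-status term, no treatment-by-panel term, no panel estimate and no fixed weighting. One Week 8 difference is compared with 0.02 under the 55% posterior-probability rule. Table 10 in Section 9.9 varies one common donepezil effect and does not vary the mix.

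**The concern.** The plan's own rationale is that mild AD and MCI carry different OCL signals and that the mix affects the chance of success. The analysis then treats the two panels as one population and leaves the mix to enrolment.

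Two things are at stake. The first is interpretation. Section 2.2 intends the donepezil result as a benchmark for later compounds, and a pooled figure describes whatever mix happened to enrol. The second is the pass probability, quoted as about 64% without saying that it may depend on the mix.

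A change of mix is a practical possibility. Section 4.2 reports that the predecessor study took 26 months, partly because treatment-naive participants were hard to find, and the synopsis plans about 16 months here. The document history records that Amendment 04 lowered the CDR sum-of-boxes threshold for MCI. The documents do not say which panel recruits faster.

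**Working it through.** **Inputs (Section 9.9).** Donepezil n = 24, SD 0.07; placebo n = 12, SD 0.06, mean change 0. Success: posterior probability of a difference above 0.02 exceeds 55%.

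**Step 1: reproduce Table 10.** As a normal approximation to the Section 9.6 rule:

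- SE = √(0.07²/24 + 0.06²/12) = 0.02245
- pass probability = Φ((δ − 0.02)/SE − z₀.₅₅), with z₀.₅₅ = 0.126

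| True effect δ (points) | Table 10, P = 55% | Approximation | Simulation of the Section 9.6 algorithm (4,000 trials) |
|---|---|---|---|
| 2.0 | 0.456 | 0.450 | 0.441 |
| 2.5 | 0.532 | 0.539 | 0.531 |
| 3.0 | 0.635 | 0.625 | 0.620 |
| 3.5 | 0.713 | 0.706 | 0.704 |
| 4.0 | 0.778 | 0.778 | 0.775 |

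All 15 cells of Table 10 agree with the approximation within 2 points. The stated power is sound for one common effect.

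**Step 2: let the effect differ by panel.** With 2:1 allocation in each panel, the mild-AD share w is the same in both arms, so

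- pooled δ = w·δ_AD + (1 − w)·δ_MCI

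The documents give no size for δ_AD − δ_MCI. The gaps below are assumptions. Each row is anchored so that the pooled effect is 3.0 points at 24 MCI and 12 mild AD, with SDs and arm totals as planned. Entries are pass probabilities from the approximation, by number of mild-AD participants out of 36.

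| Gap (points) | δ_MCI / δ_AD | 0 AD | 6 AD | 12 AD | 18 AD |
|---|---|---|---|---|---|
| 0 | 3.0 / 3.0 | 0.625 | 0.625 | 0.625 | 0.625 |
| 1 | 2.67 / 3.67 | 0.568 | 0.597 | 0.625 | 0.653 |
| 1.5 | 2.5 / 4.0 | 0.539 | 0.583 | 0.625 | 0.667 |
| 3 | 2.0 / 5.0 | 0.450 | 0.539 | 0.625 | 0.706 |

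For gaps of 1 to 3 points, going from 12 to 6 mild-AD participants costs about 3 to 9 points of pass probability, and going to 18 gains about 3 to 8. The 0 AD column is an extreme in which the recruitment effort fails entirely.

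**Step 3: precision of panel estimates, with the same SDs.**

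- MCI at 24:12 (16 donepezil, 8 placebo): √(0.0049/16 + 0.0036/8) = 0.0275, about 2.8 points
- Mild AD at 24:12 (8, 4): √(0.0049/8 + 0.0036/4) = 0.0389, about 3.9 points
- Mild AD at 30:6 (4, 2): √(0.0049/4 + 0.0036/2) = 0.055, or 5.5 points

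**Step 4: precision of a difference standardised to 2/3 MCI and 1/3 mild AD.** SE = √((2/3)²·SE_MCI² + (1/3)²·SE_AD²).

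- 24:12: 0.02245, equal to the pooled SE
- 27:9: 0.02287, 1.8% larger
- 30:6: 0.02460, 9.5% larger

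**The case against.** The strongest reply is that nothing is broken. Several parts of it stand.

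- **No contradiction between sections.** A reader might infer that Section 6.3.1 cancels a hard minimum set in Section 4.1. It does not. The 12 is worded as an effort, and Section 4.1 itself allows the adjustment in its next sentence. What remains is an ambiguity, because the same paragraph goes on to treat the number as something to be ensured.
- **No bias.** With 2:1 randomisation inside each panel, the donepezil-placebo comparison is valid at any mix. The stated population is MCI and mild AD combined, and every average effect depends on case mix.
- **Both directions are open.** More mild AD is allowed too, and under the same premise it raises the pass probability.
- **The premise is looser than a difference in means.** A more robust signal could mean lower variability. In that case the mix would move precision and the pass probability, but not the mean effect being estimated.
- **Sampling error is larger.** Under a 3-point gap, 6 instead of 12 mild-AD participants moves the pooled effect by 0.5 points, about 0.22 of the 2.25-point SE.
- **Panel estimates are weakest when most wanted.** At 30:6 the mild-AD SE is 5.5 points.

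The planned exploratory work is only a partial answer. Section 3 compares response by plasma-biomarker status, which Section 4.2.1.5.2 describes as post hoc on a biomarker panel not yet chosen. It is not a comparison of MCI with mild AD. The reply does not explain why the randomisation factor is absent from the model or why no panel result is pre-specified.

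**Conclusion.** The concern holds as an omission in the analysis plan. It is not an error in the design or in Table 10. Section 9.6 leaves out the stratification factor and offers only a pooled Week 8 difference, while Section 4.1 gives reasons to expect the panels to respond differently. If they do, the pooled result's target population and its pass probability both depend on the enrolled mix.

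The size rests on assumptions: a pure difference in mean effect, planned SDs at every mix, a total of 36, a pooled effect of 3.0 points at 24:12, and a panel gap of 1 to 3 points that the documents do not supply. On these, the pass probability falls by about 3 to 9 points with 6 mild-AD participants and rises by about 3 to 8 with 18. With no gap, the mix does not matter.

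A reader might go further and say that recruitment speed decides the primary result, or that panel estimates would reveal a platform that works in mild AD after a pooled failure. Neither is supported: the shift is small against sampling error, and the panel estimates are too imprecise.

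**What to change.** 1. Keep the pooled Week 8 difference and the 55% rule as primary.
2. Add disease status, as randomised, to the Section 9.6 primary model. As a main effect this is one extra parameter.
3. Pre-specify, as supplementary and descriptive, the Week 8 donepezil-placebo difference with its interval in each panel, from a model with panel-by-treatment-by-week terms.
4. If both panels have enough participants in each arm, also report the difference standardised to the Table 4 mix (2/3 MCI, 1/3 mild AD). State the minimum cell size beforehand, since the estimate is unavailable with an empty panel and fragile with cells as small as 2.
5. State in Section 6.3.1 whether the target of 12 binds. This is clarification only. Making it binding could slow enrolment, and that trade-off is the sponsor's.

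The cost is SAP wording and one additional model fit on data already collected. The interaction model adds about 8 fixed-effect parameters for 36 people, which is a reason to keep it supplementary. Panel intervals will be wide, and the report should say that they serve interpretation and benchmarking and do not replace the pooled decision.
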